## Appendix 2. Alpha Allocation Approach

There are 2 test statistics in the study design, denoted by  $Z_k$  for  $k$ th population (1 = overall; 2 = subgroup population [including subjects who are in the FAS whose duration of RSV symptoms prior to the first dose of study medication is  $\leq$  median of the distribution of duration of RSV symptoms in the overall FAS population] with prevalence  $b_1$ ). Specifically,  $b_1 = 0.5$  for 50th percentile threshold.

For alpha spending across the 2 tests for the primary endpoint of time-weighted average change in viral load from baseline to Day 7, the following rules are implemented, where  $c_k$  denotes the rejection boundary for the  $k$ th population:

- Pre-fix rejection boundaries ( $c_1 = 2.054$ ) for the final analysis in the overall population

$\tilde{Z} = (Z_1, Z_2)$  is a vector of standardized test statistics that follow a multivariate normal distribution with mean  $\tilde{\mu} = (\mu_1, \mu_2)$ . For a very large clinical trial and assuming no prognostic or predictive effect of duration of RSV symptoms prior to the first dose on the primary endpoint, the variance-covariance matrix for the vector  $\tilde{Z}$  can be shown to be:

$$\Sigma = \begin{pmatrix} 1 & \sqrt{b_1} \\ \sqrt{b_1} & 1 \end{pmatrix}$$

Under the null hypothesis,  $\tilde{\mu} = (0, 0)$ . Given the above rules and the variance-covariance matrix  $\Sigma$ , the table below presents the rejection boundaries for the final analysis, which can be numerically calculated such that the overall type I error rate is maintained at the 2-sided 0.05 level.

### Rejection Boundaries

Analysis Population/Subset	Final Analysis	
	Z scale	p-value
Overall population	2.054	0.04
Subgroup population ( $b_1 = 0.5$ )	2.379	0.017

### **Appendix 3. Cardiac Adverse Events of Interest**

The following search criteria are used to identify cardiac adverse events:

- All PTs from Cardiac disorders SOC
- Narrow scope PTs from the below SMQs, and associated sub-SMQs:
  - Cardiac arrhythmias (SMQ)
  - Cardiac failure (SMQ)
  - Cardiomyopathy (SMQ)
  - Ischaemic heart disease (SMQ)
  - Torsade de pointes/QT prolongation (SMQ)
- Select PTs from HLTs:
  - Cardiac histopathology procedures,
  - Skeletal and cardiac muscle analyses,
  - Arterial therapeutic procedures (excl aortic),
  - ECG investigations, Cardiac function diagnostic procedures,
  - Heart rate and pulse investigations

Duplicate PTs are removed where necessary.

#### Appendix 4. Sample SAS Code for Negative Binomial Model

The following model statement may be used for the analyses of number of hospitalization day, ICU-free day, and ventilator-free day described in Section 6.3.2:

```
proc genmod data=dataset;  
  class trt strata;  
  model count = trt strata / offset=logt dist=NB;  
run;
```

where logt is the offset parameter defined as the natural logarithm of study duration for each subject to account for potential differential study durations due to early discontinuations.

In the event that the negative binomial model fails to converge, a zero-inflated negative binomial model may be fit (dist=ZINB).

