1. INTRODUCTION

1.1. Background

Respiratory syncytial virus (RSV), a member of the family *Paramyxoviridae*, is an enveloped virus with a negative single-strand ribonucleic acid (RNA) genome. The RSV genome encodes 11 proteins, including 3 surface glycoproteins (F, G, and SH) and several proteins that comprise the viral RNA polymerase complex (N, P, L, and M2-1). Two major antigenic subgroups of RSV are known, RSV A and RSV B, that differ primarily in the genetic sequence of the G glycoprotein while maintaining a higher degree of homology across other parts of the genome. Both subgroups show comparable pathogenicity and can co-circulate in the same community during a seasonal epidemic, but their individual prevalence usually varies from season to season.

While RSV infection is commonly recognized as an important virus affecting pediatric patients, it is also an important cause of respiratory disease in the adult population. Those at particular risk include immunosuppressed adults, such as recipients of a solid organ transplant, especially those with a lung transplant (LT). Each winter, up to 12% of LT patients are infected with RSV {[Federman 2003](#)}, {[Weinberg et al 2010](#)} resulting in a mortality rate as high as 10% to 20% {[Palmer et al 1998](#)}, {[McCurdy et al 2003](#)}, {[Hopkins et al 2008](#)}. Respiratory viral infections, including RSV, are associated with the development of chronic lung allograft dysfunction (CLAD), the most recognized form being bronchiolitis obliterans syndrome (BOS) {[Vu et al 2011](#)}, {[Khalifah et al 2004](#)}. Multiple studies suggest the incidence of BOS is higher after a respiratory viral infection, with RSV specifically implicated {[Federman 2003](#)}, {[Khalifah et al 2004](#)}, {[Bridges et al 1998](#)}, {[Palmer et al 1998](#)}, {[Hayes et al 2012](#)}, {[Hopkins et al 2008](#)}. It is hypothesized that these viral infections lead to graft rejection through the triggering of an alloreactive immune response against tissue antigens {[Koehn et al 2006](#)}. BOS is of particular concern as it carries a substantial associated morbidity and mortality in LT patients.

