15.9.2.1.3	Time-Weighted Average Change in FLU-PRO Total Score from Study Baseline to Day 7	Subjects in FAS with at Least One Postbaseline FLU-PRO Score (Sensitive Analysis)
15.9.2.2.1	Percent Change from Study Baseline in Forced Expiratory Volume in 1 second (FEV 1 ) % Predicted Value at Day 28	Full Analysis Set
15.9.2.2.2	Percent Change from Study Baseline in Forced Expiratory Volume in 1 second (FEV 1 ) % Predicted Value at Day 28	Per Protocol Analysis Set
15.9.3.1.1	RSV Viral Load (log 10 copies/ml) and Change from Baseline in the Nasal Samples by Visit	Full Analysis Set
15.9.3.1.2	RSV Viral Load (log 10 copies/ml) and Change from Baseline in the Nasal Samples by Consent for Participating in the Extend Viral Load Monitoring	Full Analysis Set
15.9.3.2	Time-weighted Average and Time-weighted Average Change from Baseline in Nasal RSV Viral Load (log 10 copies/ml) by Visit	Full Analysis Set
15.9.3.3.1	Proportion of Subjects with Detectable RSV in the Nasal Samples by Visit	Full Analysis Set
15.9.3.3.2	Proportion of Subjects with Detectable RSV in the Nasal Samples by Consent for Participating in the Extend Viral Load Monitoring	Full Analysis Set
15.9.3.4	Percent and Actual Change from Baseline in FVC on Absolute Value (Liter) and % Predicted Value at Day 28/End of Study	Full Analysis Set
15.9.3.5	Proportion of Subjects Experienced ≥ 10% drop from Baseline of Either FEV 1 or FVC (Based on Both Absolute [liters] and % Predicted Measures) by Day 28/End of Study	Full Analysis Set
15.9.3.6	FLU-PRO Score and Change from Baseline by Visit	Full Analysis Set
15.9.3.7	Time-weighted Average and Time-weighted Average Change in FLU-PRO Total Score by Visit	Full Analysis Set
15.9.3.8.1	Number of Days Admitted to the Hospital through Day 28/End of Study	Full Analysis Set
15.9.3.8.2	Number of Hospital-free Days through Day 28/End of Study	Full Analysis Set
15.9.3.9.1	Number of Days Admitted to the ICU through Day 28/End of Study	Full Analysis Set
15.9.3.9.2	Number of ICU-free Days through Day 28/End of Study	Full Analysis Set

Table Number	Title	Analysis Set
15.9.3.10	Proportion of Subjects Developing Respiratory Failure Which Require Noninvasive or Invasive Mechanical Ventilation through Day 28/End of Study	Full Analysis Set
15.9.3.11	Number of Ventilator-free Days through Day 28/End of Study	Full Analysis Set

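### The negative binomial model offered for ICU-free and ventilator-free days does not suit counts capped by follow-up: its standard errors are too wide, and the scoring of deaths needs confirming

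*SAP*

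**What the plan says.** SAP Appendix 4 introduces its sample code with: "The following model statement may be used for the analyses of number of hospitalization day, ICU-free day, and ventilator-free day described in Section 6.3.2". The code is "model count = trt strata / offset=logt dist=NB", a log-link model with treatment and strata. The offset is explained as "where logt is the offset parameter defined as the natural logarithm of study duration for each subject to account for potential differential study durations" arising from early discontinuation; death is not mentioned. The one fallback is "In the event that the negative binomial model fails to converge, a zero-inflated negative binomial model may be fit".

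The SAP table list (Section 13.1) includes "Number of ICU-free Days through Day 28/End of Study" and "Number of Ventilator-free Days through Day 28/End of Study", both in the Full Analysis Set. The definitions and methods for exploratory endpoints (SAP Section 6.3) are redacted. The public text therefore does not show how a death is scored, or whether study duration stops at death.

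**The concern.** Hospitalization days are mostly zeros and small numbers with a right tail, and a negative binomial is a reasonable form for them. Free days are the mirror image: the best outcome is the maximum, and the tail runs downwards. Protocol Section 4.3 excludes subjects who need invasive ventilation or vasopressors for shock, so many subjects should sit at or near 28 free days. That is an inference, because the documents give no ICU or ventilation rates.

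Three things follow.

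- The count can never exceed the exponentiated offset, yet the model allows any value and forces the variance to be at least the mean.
- The zero-inflated fallback is triggered by non-convergence and adds mass at 0, not at 28.
- Dividing by each subject's own duration can remove the penalty for dying early, depending on the redacted definition.

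At stake is whether these two tables can show a real difference between arms, in either direction, in a trial with about 51 evaluable subjects.

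**Working it through.** The plan states no figure for these endpoints, so there is none to reproduce.

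**Inputs from the documents.** 34 and 17 evaluable subjects (Protocol Section 8.9); 28 days of follow-up (Protocol Section 3.2); the model in SAP Appendix 4.

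**Assumptions, not in the documents.** Ventilation in 2% to 40% of subjects. Ventilated days, when ventilated, are 1 plus a geometric variable with mean 8, capped at 28. Deaths are 0% or 10% per arm under the null, with day of death uniform from 3 to 27.

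**Step 1: closed form, no deaths.** The smallest SD per subject that the model allows is √mean (the Poisson limit). If every subject scored exactly 28 the true SD would be 0, yet the model SE of the log rate ratio would still be √(1/(34×28) + 1/(17×28)) = 0.056.

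Under the assumptions, ventilated days have mean 8.78 and mean square 121.6. For ventilation rate p, free days have mean 28 − 8.78p and variance 121.6p − (8.78p)².

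| p | mean | true SD | √mean | √mean ÷ true SD |
|---|---|---|---|---|
| 2% | 27.82 | 1.55 | 5.27 | 3.40 |
| 5% | 27.56 | 2.43 | 5.25 | 2.16 |
| 10% | 27.12 | 3.37 | 5.21 | 1.54 |
| 20% | 26.24 | 4.61 | 5.12 | 1.11 |
| 40% | 24.49 | 6.02 | 4.95 | 0.82 |

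Up to 20% the data vary less than the model permits. At 40% they vary more, and the dispersion parameter can absorb it.

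**Step 2: simulation of the fitted model.** 800 to 1,000 trials per scenario; maximum likelihood with treatment, one binary stratum and the log-duration offset; Wald test at two-sided 0.05. Days counted only while alive:

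| p | model SE ÷ true SD | null rejection |
|---|---|---|
| 5% | 2.0 to 2.3 | 0% to 0.1% |
| 10% | 1.5 to 1.6 | 0.1% to 0.6% |
| 20% | about 1.2 | 0.8% to 1.6% |
| 40% | 1.06 to 1.08 | 3.8% to 4.8% |

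At 2% the SE ratio is 3.4 to 3.5. At 10% or less, 95% to 100% of fits collapse to Poisson. If deaths (10% per arm) instead score 0 over a fixed 28 days, the SE ratio is 1.5 to 1.7 and rejection 0.3% to 0.9% for p from 5% to 40%. The misfit therefore does not depend on the redacted death rule.

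A second simulation (600 trials per scenario, no deaths) put 70% to 90% of subjects at 28 and the rest uniform on 14–27 or 0–10. Model SE against true SD was 0.073/0.065 = 1.12, 0.071/0.059 = 1.20, 0.108/0.088 = 1.23 and 0.110/0.091 = 1.21. Rejection was 1.5% to 2.5%; Wilcoxon gave 3.5% to 4.8%.

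**Step 3: what the offset does to a death.** A subject who dies on Day 5, never ventilated, gets:

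- 5/5 = 1.00 if days are counted while alive and duration stops at death. This equals an event-free survivor (28/28 = 1.00) and beats a survivor ventilated for 4 days (24/28 = 0.86).
- 5/28 = 0.18 if days are counted while alive and duration is fixed at 28.
- 0 if deaths score zero.

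Under the first rule, with 20% deaths on active and none on placebo and p from 5% to 20%, the mean rate ratio is 0.997 to 0.998 and the model rejects in 0% to 2% of trials. An unstratified rank-sum test with death ranked worst rejects in 28% to 43% of the same trials, and in 3.6% to 5.6% under the null (10% deaths per arm).

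**The case against.** A reader might infer that the plan scores an early death as a perfect outcome. The documents do not support that as a fact. It needs two conditions, days counted while alive and duration ending at death, and both belong to text that is blacked out. A rule scoring deaths as 0, or fixing duration at 28, removes the result. Redacted text cannot be called missing.

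A reader might also take wrong error bars to mean false positives. Type I error was not inflated in any scenario tried; the error runs the other way.

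Nor would excess deaths disappear from the report. SAP Section 7.1.6 summarises deaths through Day 28 by arm, and respiratory failure has its own table (15.9.3.10). The mortality of up to 10% to 20% in Protocol Section 1.1 is a literature upper range, not a forecast for this trial.

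The stakes are limited. Appendix 4 points to the exploratory methods section, the alpha-controlled secondary endpoints are FLU-PRO and FEV₁ only, and the code is a sample that may be used. The size of the misfit depends on assumed event rates. The zero-inflated fallback could suit hospitalization days, which share the appendix.

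All of this stands and sets the priority. It does not make an unbounded count model suitable for a count bounded by its own offset.

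**Conclusion.** Wrong as written for the error bars; low priority. For ICU-free and ventilator-free days the model in SAP Appendix 4 is misspecified. With assumed ventilation of 5% to 20%, its standard errors are about 1.2 to 2.3 times too large. Null rejection over both simulation designs is about 0% to 2.5% against 5%. It nears nominal only when events are common (about 40%) and days are counted while alive. The consequence is lost power and intervals that are too wide, and the zero-inflated fallback does not address a pile-up at the maximum.

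The event rates and lengths of ventilation are assumptions. The simulations were framed as ventilation; the same reasoning applies to ICU-free days to the extent that they too cluster at 28. The scoring of early deaths is a conditional question for the sponsor, not an established defect.

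**What to change.** In SAP Appendix 4, restrict the negative binomial to number of hospitalization days. For ICU-free and ventilator-free days, use:

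- a fixed 28-day horizon with no offset;
- the stratified Wilcoxon rank sum test already named in SAP Section 6.1.2;
- deaths by Day 28 ranked worst, unless the redacted section already sets a rule, in which case confirm that an early death cannot tie with an event-free survivor;
- a stated rule for subjects who withdraw alive before Day 28, since dropping the offset removes the only visible provision for them. One option is to report bounds, with the unobserved days counted first as all free and then as none free.

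The change covers only the two free-day endpoints that Appendix 4 names.

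The cost is a few lines of SAP wording and simpler code. The rate-ratio estimate is lost; medians and quartiles by arm can accompany the test. Ranking death worst is a choice of estimand, so the SAP should state it as one.

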## Appendix 5. Sample SAS Code for MMRM Model

The following model statement can be used for the analyses of viral load and FLU-PRO as described in Section 6.3.2:

```
proc mixed data=change;  
  class trt visit subjid strata;  
  model change = baseline strata trt visit trt*visit / s ddfm=kr;  
  repeated visit / type=un subject=subjid(trt);  
  lsmeans trt*visit / cl;  
run;
```

Note that since the response variable is change from baseline, the Visit 2 (baseline) value will always be 0 and should not be included in the above model.

An unstructured covariance will be assumed (`type=un`); if there are convergence or model fitting issues, then the alternative covariance structure of Toeplitz will be assumed (`type=toep`).

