The time-weighted average change in FLU-PRO score from Day 1/Baseline through Day 7 will be analyzed using an ANCOVA model with the baseline FLU-PRO score value and stratification factors as covariates.

The percent change in FEV₁% predicted values from Day 1/Baseline through Day 28/End of Study will be analyzed using an ANCOVA model with study baseline FEV₁% predicted value and stratification factors as covariates. The percent change in FEV₁% predicted values will be calculated as the difference of FEV₁% predicted values at Day 1/Baseline through Day 28/End of Study, divided by study baseline FEV₁% predicted value and multiplied by 100. In order to account for the multiple hypotheses testing across the primary and secondary endpoints, a sequential testing procedure will be used to control the overall Type 1 error rate of 0.05. The co-primary endpoint analyses will serve as the gatekeeper for the secondary analyses conducted within each population.

Analyses of exploratory endpoints are discussed in Section 8.5.3. Continuous endpoints will be analyzed using an ANCOVA model with corresponding baseline value and stratification factor as covariates. Categorical endpoints will be analyzed by Cochran-Mantel-Haenszel test adjusted for stratification factors. Continuous endpoints with repeated measures may also be analyzed based on a linear mixed-effects model with repeated measures (MMRM).

All endpoints will be summarized using descriptive statistics (sample size, mean, standard deviation [SD], median, Q1, Q3, minimum, and maximum) for continuous data and by the number and percent of subjects for categorical data.

Data from the Optional Registry portion of the study will be summarized descriptively. Statistical hypothesis testing will not be conducted. Nominal significance will be cited for descriptive purposes only. All continuous variables will be summarized using descriptive statistics (n, mean, standard deviation, and median, Q1, Q3, minimum, maximum) by visit. All categorical variables will be summarized by number and percentage of subjects in each categorical definition.

Pharmacokinetic

Concentrations of presatovir in plasma will be determined using a validated bioanalytical assay. Descriptive statistics (eg, n, mean, standard deviation, %CV, median, and range) will be calculated for each sampling time. The pharmacokinetic/pharmacodynamic (PK/PD) relationship may be explored as appropriate.

Power and sample size

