#### 6.1.2. Analysis for the Co-Primary Efficacy Endpoints

The co-primary analyses will test the 2 null hypotheses in the following sequence:

- $H_{01}$ : There is no difference between presatovir and placebo in the time-weighted average change in RSV  $\log_{10}$  viral load from Day 1 to Day 7 in the FAS
- $H_{02}$ : There is no difference between presatovir and placebo in the time-weighted average change in RSV  $\log_{10}$  viral load from Day 1 to Day 7 in the FAS with whose duration of RSV symptoms prior to the first dosing date of study medication is  $\leq$  median of the symptom duration distribution in the overall FAS population

To test the null hypothesis above, a parametric analysis of covariance (ANCOVA) model with corresponding baseline viral load and stratification factors (treatment of RSV infection with ribavirin and use of palivizumab or IVIG) as covariates will be used, at a 2-sided 0.05 level. Adjusted means and 95% confidence intervals (CIs) will be provided. The stratified Wilcoxon rank sum test will be implemented as a sensitivity analysis. The tests will be 2-sided with significance levels specified in Section 3.5.

Viral load values below the limit of detection (LOD) will be assigned as 0 if it is reported in the form of 'not detected'. A value of 1 unit less than the LOQ will be used for analysis if the viral load is reported in the form of "< x" (where x is considered the LOQ). Viral load data will be transformed using the base 10 logarithm for the analyses and summaries. To account for 0 values, 1 will be added to each viral load measurement before being transformed.

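### The sample repeated-measures model for viral load shares one baseline slope across all visits, while the SAP's coding of cleared virus makes that slope steepen over time: a minor, cheaply corrected loss in a supportive analysis

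*SAP*

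**What the plan says.** SAP Appendix 5 introduces its code with "The following model statement can be used for the analyses of viral load and FLU-PRO" and points to Section 6.3.2, which is redacted. The fixed effects are "model change = baseline strata trt visit trt*visit". The accompanying note confirms that the outcome is a change score ("since the response variable is change from baseline") and leaves the baseline visit out. On the covariance it says "An unstructured covariance will be assumed", with Toeplitz as the fallback. The reported quantities come from "lsmeans trt*visit / cl", that is, one adjusted mean per arm per visit.

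SAP 6.1.2 fixes the viral-load scale: "Viral load values below the limit of detection (LOD) will be assigned as 0" when reported as not detected, and 1 is added to every value before taking log10.

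The protocol synopsis makes the repeated-measures model optional for continuous endpoints. The protocol schedules central nasal sampling after baseline on Days 3, 5, 7, 9, 14, 21 and 28. Appendix 5 does not list the visits that enter the model. No visible text adds a baseline-by-visit term.

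**The concern.** The model lets the treatment effect change freely over time but forces baseline viral load to act identically at every visit. The SAP's own coding works against that. Early on, most subjects still shed and nothing ties change to baseline. Later, every cleared subject's change is minus the baseline value. A single coefficient must compromise between the two.

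A by-visit model is read for the time course of the effect. If the arms differ by chance at baseline, a slope that is too steep at one visit and too flat at another leaves part of that difference in the adjusted contrasts, in some scenarios with opposite signs early and late. It also leaves explainable variance in the residual. At 34 versus 17 subjects, chance imbalance is not negligible.

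**Working it through.** The documents give no figure for this model, so there is none to reproduce.

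**Slope once cleared.** For baseline B copies/mL, an undetected sample gives change = log10(0+1) - log10(B+1) = -log10(B+1). For B = 10^4, 10^6 and 10^8 this is -4, -6 and -8: a slope of exactly -1 among cleared subjects. The slope for a whole visit only approaches -1 as the cleared share rises.

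**Effect of a shared slope.** Let b_v be the slope at visit v, b_c the common slope and d the baseline difference, presatovir minus placebo. The shared-slope model leaves about (b_v - b_c) × d in the treatment difference. Its variance is about that of the visit-specific model plus (b_v - b_c)² × Var(d).

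**Chance imbalance.** SD(d) = SD_baseline × √(1/34 + 1/17) = 0.297 × SD_baseline: 0.30, 0.45 and 0.59 for baseline SD 1.0, 1.5 and 2.0. With baselines truncated as below, the simulated values are 0.30, 0.44 and 0.56, and |d| exceeds 0.5 log10 in 10%, 27% and 38% of trials.

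**Simulation.**
- From the SAP: 34 versus 17 subjects, and the planning values for placebo time-weighted average change to Day 7 (DAVG7), mean -1.5 and SD 1.2 (Section 1.3).
- Assumed: the seven protocol visits, complete data, no treatment effect, baseline mean 6 log10 truncated at 2.5, detection limit 2 log10, assay noise SD 1, one binary stratum, and subject-specific linear decline per day. In Set A the decline has mean 0.42, SD 0.40 and minimum 0.03. In Set B it has mean 0.45, SD 0.35 and minimum 0.12.
- Both models were fitted with unstructured covariance to 2000 trials per row.
- DAVG7 came out at -1.44 (SD 1.16 to 1.19) in Set A and about -1.53 (SD 1.06 to 1.08) in Set B.

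| Set, baseline SD | Common slope | Slope Day 3 / Day 14 / Day 28 | Variance ratio, printed model to model with baseline*visit, Day 3 / 7 / 14 / 28 | SE ratio Day 3 / Day 28 |
|---|---|---|---|---|
| A, 1.0 | -0.05 | 0.06 / -0.45 / -0.68 | 1.01 / 0.99 / 1.02 / 1.07 | 1.00 / 1.03 |
| A, 1.5 | -0.04 | 0.06 / -0.44 / -0.67 | 1.02 / 0.99 / 1.05 / 1.16 | 1.01 / 1.08 |
| A, 2.0 | -0.02 | 0.06 / -0.43 / -0.67 | 1.02 / 0.99 / 1.09 / 1.26 | 1.01 / 1.12 |
| B, 1.0 | -0.34 | 0.06 / -0.48 / -0.72 | 1.11 / 1.00 / 0.99 / 1.08 | 1.05 / 1.04 |
| B, 1.5 | -0.32 | 0.06 / -0.47 / -0.73 | 1.21 / 1.02 / 1.00 / 1.18 | 1.10 / 1.09 |
| B, 2.0 | -0.27 | 0.06 / -0.45 / -0.72 | 1.22 / 1.03 / 1.02 / 1.32 | 1.10 / 1.15 |

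The SE ratio is the square root of the variance ratio. Further runs with DAVG7 SD about 1.2 to 1.3 gave SE inflation of roughly 3% to 13% at Day 28 and 3% to 10% at Day 3.

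**Residual shift.** At baseline SD 1.5, the simulated shift per 1 log10 of imbalance is +0.10 at Day 3 and -0.63 at Day 28 in Set A, and +0.38 and -0.39 in Set B. A one-SD imbalance (0.44) therefore moves the Day 28 difference by -0.63 × 0.44 = -0.28 (Set A) or -0.39 × 0.44 = -0.17 (Set B). The empirical standard errors there are 0.73 and 0.44. With baseline*visit, the shift per 1 log10 is at most 0.06 in size at any visit.

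**Cross-check, Set A, SD 1.5, Day 28.** √(0.676² + 0.28²) = 0.73, against a simulated 0.727 for the printed model. The variance formula accounts for the loss.

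**Validity.** Mean null differences lie within 0.025 log10 of zero under both models. In the same cell, the model-based SE is 0.709 against an empirical 0.727 for the printed model, and 0.659 against 0.676 with the added term. The ratio is about 0.975 both times, so the missing term does not make the standard errors misleading.

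**The case against.** The strongest reply is that this is sample code for an optional analysis and that the section governing it cannot be seen. Section 6.3.2 may already specify the term or limit the visits. If the model stopped at Day 9, the slopes above would run only from about 0.06 to -0.19 and there would be little to correct. That stands, and it limits the weight of the point.

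Several stronger readings are tempting, and the documents do not support them.

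- *The by-visit differences are biased.* They are not, averaged over randomizations. The shift depends on chance imbalance, and the unstructured covariance carries the misfit into the standard errors.
- *Every visit is affected.* In the table, variance ratios at Days 7 and 14 lie between 0.99 and 1.09. Which visits suffer depends on the kinetics. Protocol 1.1 reports that shedding ended within 7 days for most subjects in earlier lung-transplant trials, while 1.4 cites 21 days or longer in immunosuppressed patients. If about half or more are undetected by Day 7, SE inflation at Days 14 to 28 falls to 3% or less and the loss moves to Day 3.
- *The precision loss is large.* Across a wider range of assumed decline rates the Day 28 variance ratio reached 1.71 (SE ratio √1.71 = 1.31), but those rates lie further from the SAP's planning values.
- *The confirmatory results are at risk.* The co-primary and both secondary analyses are separate ANCOVAs, each estimating its own baseline slope.
- *FLU-PRO has the same defect.* The -1 argument comes from the viral-load coding. SAP 6.2.1 defines FLU-PRO as a mean item score without stating a floor. Inclusion criterion 3 admits worsening of chronic symptoms, so resolution to zero cannot be presumed. Nothing was computed for FLU-PRO.

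**Conclusion.** The point holds as a minor improvement. Under the SAP's coding, the slope of change on baseline must steepen as virus clears, and the printed model cannot follow it. The cost is imperfect adjustment for chance imbalance and some lost precision at the visits that the common slope fits worst.

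Near the planning values, with baseline SD 1 to 2, the standard error rises by roughly 3% to 13% at Day 28. Set B at baseline SD 2.0, whose DAVG7 SD is slightly below the planned 1.2, reaches 15%. At Day 3 the rise is up to about 10%, and about 1% or less in Set A. It is close to zero at the middle visits. All of these sizes rest on assumed kinetics, baseline spread and detection limit. The direction rests only on the SAP's coding and a rising cleared share. Only a supportive by-visit analysis is affected.

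**What to change.** Before the blind is broken, change the viral-load statement in SAP Appendix 5 to `model change = baseline visit baseline*visit strata trt trt*visit`, keeping the existing options, and name the visits that enter the model. If Section 6.3.2 already specifies the interaction, align the appendix with it.

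The cost is one term and up to 6 degrees of freedom (7 visits - 1). Where the slopes hardly differ, almost nothing is lost: no variance ratio in any scenario fell below 0.98. Settling this before unblinding avoids choosing the covariate form after seeing the data. Using the same term for FLU-PRO is reasonable for consistency, but the viral-load coding is not a reason for it.
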